ALT or AST \geq 5× but < 10× ULN, and Total and direct bili < 1.5× ULN, and INR < 1.3 × ULN	Continue dosing Monitor liver panel weekly If ALT/AST fall to <1.5× ULN, stop weekly monitoring	
ALT or AST \geq 10× ULN, and Total and direct bili < 1.5× ULN, and INR < 1.3 × ULN	Interrupt dosing Monitor liver panel weekly If ALT/AST fall to <5× ULN, restart dosing; if ALT/AST fall to <1.5×, stop weekly monitoring	If the event does not resolve in 4 weeks or recurs, consult medical monitor about discontinuing study medication
ALT or AST \geq 5× ULN, and Total or direct bili \geq 1.5× ULN, or INR \geq 1.3 × ULN		Discontinue study medication
ALT or AST $< 5 \times$ ULN, and Total or direct bili $\ge 1.5 \times$ ULN, or INR $\ge 1.3 \times$ ULN	Interrupt dosing Monitor liver panel weekly If total and direct bili fall to <1.5 × ULN and/or INR falls to < 1.3× on 2 consecutive tests, stop weekly monitoring and restart dosing	If the event does not resolve in 4 weeks or recurs, consult medical monitor about discontinuing study medication

For patients with Gilbert Syndrome, the 1.5 × ULN criteria for total and direct bilirubin will be replaced with a 1.5 × ULN for direct bilirubin and there will be no monitoring criteria for total bilirubin [Fontana 2020]. Other etiologies of ALT, AST, total and direct bilirubin, and INR elevations, such liver injury induced by other drugs and other viral infections, should be ruled out and treated accordingly.

If a patient prematurely discontinues study medication on or before Day 169, the Day 169/Early termination procedures will be performed. Patients who prematurely discontinue study medication will remain in the study for follow-on study assessments.

Patients will be followed for 52 weeks after the last dose of study medication (504 days beyond Day 1 for patients who complete the 24-week Treatment Period).

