A sentinel cohort of 12 patients (6 receiving HepTcell and 6 placebo) will undergo blinded safety review by the Safety Committee 7 to 10 days after all ongoing patients in the sentinel cohort have completed the respective dose of study medication and will determine the decision to continue at that dose to the expanded cohort. Safety will be assessed in the sentinel cohort before each dose is administered to the expanded cohort. If any of the Stopping Rules in Section 7.1.1 are met in one or more patients and the event(s) is deemed possibly or probably related to HepTcell, dosing will be suspended pending DMC review. DMC recommendations may include instituting modifications to ensure the safety of continued dosing or discontinuing the study. If none of the Stopping Rules are met, randomization and dosing may continue in the expanded study cohort. Patients will be unblinded as necessary to assess the relationship between the study medication and events that meet criteria for Stopping Rules.

Safety laboratory testing (Table 3), including liver panel, for Doses 1 and 2 will be obtained during the visits conducted 7±2 days after these doses of study medication. Safety laboratory testing following Doses 3, 4 and 5 will be obtained in the interval from 7 days after dose administration and before the next dose of study medication is administered. Safety labs after Dose 6 will be assessed at the Day 169 visit. Investigators will review the eligibility of all patients prior to dosing to determine if the next treatment is to be administered. Eligibility for the next treatment will include: 1) confirmation that patients did not meet a Stopping Rule (Section 7.1.1); 2) confirmation that the pre-treatment liver parameters are within acceptable ranges for treatment (below); 3) confirmation that patients do not have a new confirmed or suspected IMC (Appendix 2). Patients not meeting these criteria will not be treated.

If abnormalities of ALT, AST, total bilirubin, direct bilirubin, or international normalized ratio (INR) are reported after dosing is commenced, the following monitoring and dosing rules will be applied:

Toxicity	Management	Discontinuation of Study Medication
ALT or AST \geq 5×but < 10 × ULN, and Total and direct bili < 1.5×ULN, and INR < 1.3 ×ULN	Continue dosing Monitor liver panel weekly If ALT/AST fall to <1.5×ULN, stop weekly monitoring	

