ALT or AST ≥ 10×ULN, and Total and direct bili < 1.5×ULN, and INR < 1.3 ×ULN	Interrupt dosing Monitor liver panel weekly If ALT/AST fall to <5×ULN, restart dosing; if ALT/AST fall to <1.5×, stop weekly monitoring	If the event does not resolve in 4 weeks or recurs, consult medical monitor about discontinuing study medication
ALT or AST \geq 5×ULN, and Total or direct bili \geq 1.5×ULN, or INR \geq 1.3 ×ULN		Discontinue study medication
ALT or AST $< 5 \times ULN$, and Total or direct bili $\ge 1.5 \times ULN$, or INR $\ge 1.3 \times ULN$	Interrupt dosing Monitor liver panel weekly If total and direct bili fall to <1.5 ×ULN and/or INR falls to < 1.3× on 2 consecutive tests, stop weekly monitoring and restart dosing	If the event does not resolve in 4 weeks or recurs, consult medical monitor about discontinuing study medication

For patients with Gilbert Syndrome, the 1.5 × ULN criteria for total and direct bilirubin will be replaced with a 1.5 × ULN for direct bilirubin and there will be no monitoring criteria for total bilirubin [Fontana 2020]. Other etiologies of ALT, AST, total and direct bilirubin, and INR elevations, such liver injury induced by other drugs and other viral infections, should be ruled out and treated accordingly.

If a patient prematurely discontinues study medication on or before Day 169, the Day 169/Early termination procedures will be performed. Patients who prematurely discontinue study medication will remain in the study for follow-on study assessments.

Patients will be followed for 52 weeks after the last dose of study medication (504 days beyond Day 1 for patients who complete the 24-week Treatment Period). AEs and concomitant medications will be recorded from the signing of informed consent to Day 169, but only MAEs, NCIs, and IMCs, which will be categorized as AEs, will be followed subsequently. Likewise, concomitant medications will be recorded through Day 169, but only immunosuppressive medications, vaccines, and new HBV treatments or medications associated with MAEs, NCIs, SAEs, hepatitis flares, or hepatic injury will be recorded beyond this point. At the end of the clinical trial, the decision about follow-on treatments and medical care will be made by the patient's medical physician or medical team in accordance with the usual standard of care.

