4.3. Rationale for Study Design

The study design replicates the general design of the prior Phase 1 study but extends treatment from 3 to 6 doses and the follow-up after the last dose of study medication from 30 to 52 weeks. These modifications will enhance the effects of study medication and provide a more extended follow-up to assess the durability of immunogenicity and AEs. Diaries will be collected for reactogenicity events at visits on Days 8 and 36, which correspond to 7±2 days after the first and second dose of study medication. A visit consisting of a targeted physical examination will be conducted 7±2 days after administration of Doses 1 and 2 of study medication. Safety laboratory testing (Table 3), including liver panel, for Doses 1 and 2 will be obtained during the visits conducted 7±2 after these doses of study medication. Safety laboratory for Doses 3, 4 and 5 will be obtained in the pre-treatment interval from 7 days after dose administration through the time that the next dose of study medication is administered. Safety labs after Dose 6 will be assessed at the Day 169 visit. Investigators will review the eligibility of all patients prior to dosing to determine if the next treatment is to be administered. Eligibility for the next treatment will include: 1) confirmation that patients did not meet a Stopping Rule (Section 7.1.1); 2) confirmation that the pre-treatment liver parameters are within acceptable ranges for treatment (Section 4.1); 3) confirmation that patients do not have a new confirmed or suspected IMC (Appendix 2). If abnormalities of ALT, AST, total bilirubin, direct bilirubin, or INR are reported after dosing is commenced, the monitoring and dosing rules of Section 4.1 will be applied. These procedures are considered sufficient to evaluate reactogenicity events, particularly after Doses 1 and 2, and guard

against hepatitis flares and liver function abnormalities that would preclude the scheduled administration of the next dose of study medication.

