- ^a Randomization may occur up to 3 working days before Day 1 (the day of first dosing) to allow for the possible preparation of study medication by a central pharmacy and shipment to the study site. If the patient is to be randomized before Day 1, the eligibility of the patient will be confirmed by a telephone visit prior to randomization. Concomitant medications AEs will also be assessed.
- b If a patient prematurely discontinues study medication before Day 169, Day 169/Early termination procedures will be performed. Patients who prematurely discontinue study medication will remain in the study for Follow-Up Period study assessments, the dates of visits adjusted to correspond to 13, 26, 39 and 52 weeks after the last dose of study medication.
- ^c A telemedicine visit would include a home visit by appropriate trained personnel to perform a target and symptom-driven physical and obtain vital signs and safety laboratories. The remaining portions of the visit may be conducted virtually by the study investigator.
- d After Day 169 or ET, only immunosuppressive medications, vaccines, and new HBV treatments or medications associated with MAEs, NCIs, SAEs, hepatitis flares, or hepatic injury will be recorded.
- ^e Measured before any blood sample collection.
- f Not required if performed within 12 months or if no fibrosis seen on liver biopsy within 2 years before screening.
- g For women of childbearing potential only. A serum pregnancy test will be obtained in lieu of a urine pregnancy test at screening.
- h Hepatitis B genotyping will be performed at screening if it has not been documented in the prior medical record.
- ¹ Serology and viral markers = HBsAg, anti-HBs, HBVDNA, pg-RNA, HBcAg, HBeAg, HBeAg antibody.
- Jif the patient has experienced an acute illness or temperature > 38°C in the 2 days prior to dosing, the administration of study medication and corresponding visit will be delayed until the illness or fever has resolved.
- k Investigators will review the eligibility of all patients to determine if the next treatment is to be administered. Eligibility for the next treatment will include 1) confirmation that patients did not meet a Stopping Rule (Section 7.1.1); 2) confirmation that the pre-treatment liver parameters are within acceptable ranges for treatment (Section 4.1); 3) confirmation that patients do not have a new confirmed or suspected IMC (Appendix 2). Patients not meeting these criteria will not be treated.

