6.4. Dosing Modifications

The sentinel cohort of 12 patients will undergo blinded safety review by the Safety Committee 7 to 10 days after all ongoing patients in the sentinel cohort have completed

the respective dose of study medication and will determine the decision to continue at that dose into the expanded cohort. Safety will be assessed in the sentinel cohort before each dose is administered to the expanded cohort. If any of the Stopping Rules in Section 7.1.1 are met in one or more patients in the sentinel cohort and the event(s) is deemed possibly or probably related to HepTcell, dosing will be suspended pending DMC review. DMC recommendations may include instituting modifications to ensure the safety of continued dosing or discontinuing the study. If none of the Stopping Rules (below) are met, randomization and dosing may continue in the expanded study cohort. Patients will be unblinded as necessary to assess the relationship between the study medication and events that meet criteria for Stopping Rules. Patients who experience events that meet criteria for Stopping Rules will permanently terminate dosing.

Monitoring and dosing rules for patients who experience liver abnormalities is described in Section 4.1.

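### The liver table restarts dosing after values that Section 6.4 says end it permanently, and INR is measured on two different scales

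*Protocol*

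**What the plan says.** **The strict rule.** Protocol 7.1.1 lists four laboratory Stopping Rules:

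- ALT or AST ≥10×ULN
- INR ≥1.3
- total bilirubin ≥1.5×ULN, in patients without Gilbert Syndrome
- direct bilirubin ≥1.5×ULN, in patients with Gilbert Syndrome

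Section 6.4 gives the consequence for the individual: "Patients who experience events that meet criteria for Stopping Rules will permanently terminate dosing". SAP 5.3.16 carries the same sentence. Section 4.1 and Table 1 footnote k add a check before each later dose. Its first item is "confirmation that patients did not meet a Stopping Rule". Acceptable liver values are a separate second item. The result of failing the check is plain: "Patients not meeting these criteria will not be treated".

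**The restart rule.** The liver table in Section 4.1, also printed in the Study Summary, has four rows. Row 2 covers ALT/AST ≥10×ULN with bilirubin and INR below threshold. It interrupts dosing, then says "If ALT/AST fall to <5×ULN, restart dosing". Row 4 covers ALT/AST <5×ULN with total or direct bilirubin ≥1.5×ULN, or INR ≥1.3×ULN. It also interrupts dosing, and once values are below threshold "on 2 consecutive tests, stop weekly monitoring and restart dosing". For Gilbert patients, "the 1.5 × ULN criteria for total and direct bilirubin will be replaced with a 1.5 × ULN for direct bilirubin". In both rows the medical monitor is consulted about discontinuation only if the event lasts beyond 4 weeks or recurs.

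**The concern.** The two instructions cannot both be followed. A patient whose ALT reaches 10×ULN has met a Stopping Rule and is finished with dosing under 6.4, but may be dosed again under row 2 once ALT falls below 5×ULN. The table is what an investigator is likely to consult when a liver result comes back abnormal, and nothing in it says that its restart wording gives way to 6.4.

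Two things are at stake. The first is safety: a patient could be dosed again after a value that the protocol elsewhere treats as ending treatment. The second is reporting. SAP 5.2.2 lists all deviations in the study report and uses them to help select the Per Protocol population. Whether a dose given after such a value is a deviation depends on which text is taken to govern.

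This point makes no claim about the DMC suspension trigger or the efficacy results.

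**Working it through.** The plan gives no figure to reproduce, because this is a matter of threshold logic. The inputs are the Stopping Rules in Protocol 7.1.1 and the four rows of the table in Section 4.1.

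**Row by row**

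| Row | Trigger | Table action | Also a Stopping Rule? | Conflict with 6.4 |
|---|---|---|---|---|
| 1 | ALT/AST ≥5 to <10×ULN, bilirubin and INR below threshold | Continue | Only if INR is ≥1.3 but <1.3×ULN | INR gap only |
| 2 | ALT/AST ≥10×ULN, bilirubin and INR below threshold | Interrupt, then restart | Always | Full |
| 3 | ALT/AST ≥5×ULN with raised bilirubin or INR | Discontinue | Often | None |
| 4 | ALT/AST <5×ULN with raised bilirubin or INR | Interrupt, then restart | Usually | Partial |

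**Row 4 trigger patterns** (assuming a laboratory INR ULN ≥1.0, so that INR ≥1.3×ULN implies INR ≥1.3)

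- Without Gilbert Syndrome there are three triggers: total bilirubin, direct bilirubin and INR. Possible patterns: 2³ − 1 = 7. All but one contain total bilirubin or INR and so meet a Stopping Rule. The exception is direct bilirubin alone, which 7.1.1 makes a Stopping Rule only in Gilbert patients. Result: 6 of 7.
- With Gilbert Syndrome there are two triggers: direct bilirubin and INR. Possible patterns: 2² − 1 = 3, and all meet a Stopping Rule. Result: 3 of 3.
- Together: 6 + 3 = 9 of 7 + 3 = 10. These are patterns, not patients.

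**INR scale.** Section 7.1.1 uses an absolute 1.3 and the table uses 1.3×ULN. The ULN values below are assumptions.

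| Assumed INR ULN | Table cut-off | Meets 7.1.1 but below the table cut-off |
|---|---|---|
| 1.0 | 1.3 × 1.0 = 1.30 | none |
| 1.1 | 1.3 × 1.1 = 1.43 | 1.30 to <1.43 |
| 1.2 | 1.3 × 1.2 = 1.56 | 1.30 to <1.56 |

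In that gap a row 1 patient is told to continue dosing. A patient with ALT/AST <5×ULN and bilirubin below threshold falls in no row at all. Separately, the Study Summary gives the Stopping Rule as INR above 1.3, and 7.1.1 as 1.3 or above, so a value of exactly 1.30 is treated differently in the two places.

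**Timing** (nominal days)

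- Laboratory tests on Day 8, Dose 2 on Day 29: 29 − 8 = 21 days, with weekly tests on Days 15, 22 and 29.
- Laboratory tests on Day 36, Dose 3 on Day 57: 57 − 36 = 21 days.
- Both intervals are shorter than the 4-week (28-day) consultation point. Row 2 needs ALT/AST to fall below 5×ULN, and row 4 needs two consecutive tests below threshold. Either can be met in time for the next scheduled dose, with no dose missed.

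**Doses.** For an event after Dose k, 6.4 gives k doses in total and the table up to 6. The difference is at most 6 − k: 5 at k = 1, falling to 1 at k = 5 and 0 at k = 6. This is a ceiling, not an expected value.

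**The case against.** The best defence is that Section 4.1 already contains the controlling rule. The check before each dose lists freedom from a Stopping Rule separately from acceptable liver values, so the table informs only the second item and cannot authorise a dose alone. On that reading the strict rule wins and the restart wording is leftover text. This largely stands as a reading of intent, and most of the text does favour the strict rule. But the restart instruction remains, nothing says that it yields, and under the strict rule it could never operate in row 2.

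A second defence runs the other way. The line in 6.4 after the permanent-termination sentence sends liver abnormalities to Section 4.1, 7.1.1 is prefaced by consultation with the DMC, and relatedness is mentioned nearby. Perhaps only related events end dosing and the table manages the rest. However, the pointer is not worded as an exception, and relatedness governs suspension of study dosing. The sentence on the individual patient carries neither condition.

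Several limits are fair:

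- The SAP sentence is a copy, not independent support.
- The 9-of-10 count depends on the INR ULN. At 0.9, an INR of 1.17 to 1.29 triggers row 4 without meeting a Stopping Rule. Above 1.0, even isolated direct bilirubin coincides with a Stopping Rule if INR lies in the gap.
- The no-missed-dose timing is clearest after Doses 1 and 2. After Doses 3 to 5, Table 1 places laboratory tests at the next dosing visit, although footnote o allows them from 7 days after the dose. The 6 − k ceiling at those doses depends on early sampling.
- SAP Section 2 reports good tolerability and no significant safety events, and the study is ending. This lowers the urgency, but it does not show that no Stopping Rule value occurred.

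**Conclusion.** The concern holds. As written, row 2 contradicts 6.4 for every patient it covers. Row 4 contradicts it in 9 of 10 trigger patterns if the laboratory INR ULN is at least 1.0. Row 3 does not conflict, and row 1 conflicts only through the INR mismatch, which opens when the ULN exceeds 1.0. The row 2 conflict needs no assumption. The number of patients affected is unknown and may be zero. This should be fixed: the correction is small, and without it doses given after a Stopping Rule value cannot be classified consistently.

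**What to change.** **Now.** Protocol 10.5 places the interim analysis after all patients have completed or stopped treatment, and SAP Section 2 says that analysis was done, so dosing appears complete. In the study report:

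- State which rule was applied.
- List each patient who met a laboratory Stopping Rule and received a later dose.
- Classify those doses in one consistent way in the deviation listing.

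Planned listings 16.2.1.2.2 (next-dose eligibility), 16.2.5.2 (drug administration) and 16.2.8.2 (biochemistry) supply the data. First confirm that INR is included in the laboratory listing used.

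**Text.** In the Study Summary, Sections 4.1 and 6.4, and Table 1 footnote k, state that a patient who meets a Stopping Rule is not dosed again. Delete the row 2 restart. Limit the row 4 restart to events that are not Stopping Rules, namely isolated direct bilirubin in patients without Gilbert Syndrome. Use one INR scale and one inequality throughout.

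**Cost.** One statement and one short patient list, or one clarifying amendment if any dosing were still under way. No extra patients, visits or tests.

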6.5. Blinding and Unblinding

The Pharmacy staff at the central or site pharmacy will be unblinded for the purpose of final drug preparation. The pharmacist will consult the IWRS for dose allocation and the Pharmacy staff will prepare each dose in compliance with the randomization list.

Due to the fact that formulations cannot be made to look identical, a blinded syringe will be used for administration.

Knowledge of the randomization list will be limited to the persons responsible for creation of the randomization list, pharmacy staff who prepare the study medications, unblinded site staff who administer the study medication and any unblinded study monitors or auditors, until all data has been entered in the electronic Case Report Form (eCRF), quality control and verification of the eCRF and assignment of patients to the analysis populations has been completed, the database has been locked, and the study formally unblinded.

Data provided to the Safety Committee will be blinded.

If unblinding is required in the interest of the safety of a patient, an Investigator will discuss the matter with the Sponsor before unblinding. In a medical emergency, the Investigator or delegate may unblind via the IWRS for that patient without prior consultation with the Sponsor. In that event, the Investigator or delegate will notify the Sponsor as soon as possible that the randomization code has been broken for the patient. If the blind is broken, the date, time, and reason must be recorded.

Patients may also be unblinded for the processing of SAEs, expedited safety reports, and the emergency unblinding of patients, as detailed in a separate Safety Management Plan.

6.6. Accountability

The Investigator (or designee) will maintain an accurate record of the receipt of each study medication as shipped by the Sponsor (or designee), including the date received. In

addition, an accurate study medication disposition record will be kept, specifying the amount dispensed for each patient and the dates of dispensation and any returns.

Sponsor approval is required for on-site destruction of all used study medication and shipment of all unused study medication back to the Sponsor at the completion of the study and once all reconciliation has occurred.

6.7. Prior and Concomitant Therapy

In the interests of patient safety and acceptable standards of medical care, the Investigator will be permitted to prescribe additional treatment(s) at his/her discretion. However, as noted below, changes in any chronically administered medications or treatments should be avoided during the Treatment Period (through Day 169).

All medications must be recorded in the patients' eCRFs from 30 days before the first dose through Day 169 or early termination (ET) from the Treatment Period, but only immunosuppressive medications, vaccines, and new HBV treatments or medications associated with MAEs, NCIs, SAEs, hepatitis flares, or hepatic injury will be recorded beyond this point through the end of the Follow-up Period (Day 505 or ET from Follow-up).

